5.2 Endpoint Variables

- Death Site reported events.
- Stroke CEC adjudicated site reported events through all follow-up time periods.
- Myocardial Infarction CEC adjudicated site reported events through the 5-year follow-up periods.
- Bowel Ischemia CEC adjudicated site reported events through the 5-year followup periods.
- Paraplegia CEC adjudicated site reported events through the 5-year follow-up periods.
- Respiratory Failure CEC adjudicated site reported events through the 5-year follow-up periods.
- Renal Failure CEC adjudicated site reported events through the 5-year follow-up periods.
- Procedural Blood Loss > 1000 mL Site reported events during initial procedure.
- Thromboembolic events CEC adjudicated site reported events through the 5-year follow-up periods.
- Type I endoleaks Core Lab reported events.
- Type III endoleaks Core Lab reported events.
- Migration Core Lab reported prosthesis or intercomponent migration.
- AAA enlargement Using Core Lab reported data, the measurement closest to 30 days after initial implant will be subtracted from the measurement closest to 365 days after initial implant.
- AAA rupture –Core Lab reported events or CEC adjudicated site reported events through the 5-year follow-up periods.
- Conversion to open repair CEC adjudicated site reported events through the 5vear follow-up periods.
- Aneurysm related mortality CEC adjudicated site reported events through the 5year follow-up periods.
- Stent fracture Core Lab reported events.
- Reintervention CEC adjudicated site reported events through the 5-year follow-up periods.
- Type II endoleak –Core Lab reported events.
- Type IV endoleak –Core Lab reported events.
- Index Procedure Time Site reported during initial procedure.
- Length of Hospital Stay Site reported during initial hospitalization.

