Number of Sites	A maximum of 56 sites located in the U.S.
	The Sponsor shall maintain an updated list of principal investigators, investigational sites, and institutions. This list shall be kept separately from this Protocol.
Expected Time to	Subject accrual – 2 years
Complete Enrollment	Follow-up – 5 years from last subject enrollment
	Total investigation duration – 10 years
	(including site initiation and closing period)
Expected Time of each Study Subject to Complete the Study	Total of 60 months for each subject to complete the study
Pre-Treatment Evaluation	 Physical exam / medical history within 30 days of procedure Serum creatinine concentration Contrast enhanced spiral CT of the abdomen and pelvis ≤ 90 days from procedure
Follow-Up Evaluations	 Follow-up conducted at one, six, and twelve months post- treatment and annually thereafter for five years to consist of: Physical examination Contrast enhanced CT scan
	 Non-contrast CT scan (1 month only)

Significant Inclusion Criteria	 AAA meeting any of the following criteria: Maximum diameter ≥ 50 mm Rapid growth (> 5 mm in a 6 month period) Non-ruptured AAA presenting with clinical symptoms Adequate anatomy to receive the CEXC Device, including: Adequate iliac / femoral access Infrarenal aortic neck diameter 16-32 mm Infrarenal aortic neck length ≥ 10 mm Aortic neck angle ≤ 90° Distal iliac artery seal zone ≥ 10 mm Iliac artery diameter 8-25 mm An Informed Consent Form (ICF) signed by subject Male or infertile female* Able to comply with Protocol requirements including following-up Life expectancy > 2 years Age ≥ 21 years * Infertile female – condition which prevents pregnancy, e.g., hysterectomy, tubal ligation or postmenopausal for greater than 1 year Subjects will be allocated to the appropriate substudy based on the aortic neck angle measurement recorded during screening.
Significant Exclusion Criteria	 Mycotic or ruptured aneurysm Known concomitant thoracic aortic aneurysm which requires surgical intervention Renal insufficiency defined as creatinine > 2.5 mg / dL or patient undergoing dialysis New York Heart Association (NYHA) class IV Aneurysmal, dissected, heavily calcified, or heavily thrombosed landing zone(s) Severely tortuous or stenotic iliac and / or femoral arteries Patient has body habitus or other medical condition which prevents adequate delineation of the aorta Participating in another investigational device or drug study within 1 year of treatment

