2.4.2 Primary Effectiveness Endpoint (each substudy)

Treatment success: Technical success (defined as successful access and deployment of all required CEXC Device components) and freedom from the following events:

- Type I endoleaks in the 12 month analysis window
- Type III endoleaks in the 12 month analysis window

- Migration ≥ 10 mm between the baseline and the 12 month analysis window
- AAA enlargement ≥ 5 mm with or without intervention between the baseline and the 12 month analysis window
- AAA rupture through the 12 month analysis window
- Conversion to open repair through the 12 month analysis window

The baseline assessment shall occur prior to the end of the one month study window for the Short Neck Substudy and within the first 90 post-operative days for the High Neck Angulation Substudy.

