5.0 Statistical Analyses

5.1 Analysis Populations

The following populations will be used in various analyses of the data collected in the AAA 13-03 study:

- 1. All Enrolled Subjects This population will consist of all enrolled Subjects
- Safety Eligible Population (each substudy) This population will consist of Initial Cohort Subjects with a follow-up visit at or after 30 days following initial CEXC Device implant procedure. Additionally, any Subjects with an eligible safety event, as defined in Section 2.4.1, even if they did not complete a follow-up visit at or after 30 days following initial procedure, will be included.

3. Primary Effectiveness Population

Short Neck Substudy - This population will consist of Initial Cohort Subjects with both post-op (no later than one month study window) contrast-enhanced CT imaging and a 12 month follow-up visit that included contrast-enhanced CT imaging. Additionally, any Subjects with an eligible effectiveness event, as defined in **Section 2.4.2**, even if they did not complete the necessary follow-up visit or imaging to otherwise be included in the population, will be included.

High Neck Angulation Substudy – This population will consist of Initial Cohort Subjects with both post-op (no later than 90 days) contrast-enhanced CT imaging and a 12 month follow-up visit that included contrast-enhanced CT imaging. If a subject without a 12 month contrast-enhanced CT imaging has post-12 month contrast-enhanced CT imaging at which there was no endpoint event identified by Core Lab (Type I Endoleak, Type III Endoleak, Migration, or Rupture) using the post 12-month contrast CT closest to the 12-month window, the subject will also be included in the analysis. Additionally, any Subjects with an eligible effectiveness

event, as defined in **Section 2.4.2**, even if they did not complete the necessary follow-up visit or imaging to otherwise be included in the population, will be included.

Secondary Effectiveness Populations (each substudy, each endpoint) - These
populations will consist of Initial Cohort Subjects with an evaluable result for the
specific variable.

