5.4 Statistical Analysis of Endpoints

One-sided exact Clopper-Pearson confidence intervals for binomial proportions (alpha=0.05) will be constructed to test the primary safety and primary effectiveness hypotheses in each substudy. The null hypothesis will be rejected if the lower bounds of the 95% confidence interval estimating device effectiveness and safety exceeds the performance goal. This is equivalent to stating that the estimated effectiveness and safety must exceed the PG with a Type I error rate (alpha) of < 0.05.

All events must meet the protocol definition and will be adjudicated through the CEC process.

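### SAP 5.2 derives AAA enlargement from the scans nearest days 30 and 365 without the windows of 2.4.2, so a 6 month scan can displace a late but valid 12 month scan

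*SAP*

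**What the plan says.** Two sections of the SAP describe enlargement.

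- **2.4.2 (definition).** Treatment success requires freedom from "AAA enlargement ≥ 5 mm with or without intervention between the baseline and the 12 month analysis window". For Short Neck it adds: "The baseline assessment shall occur prior to the end of the one month study window for the Short Neck Substudy". For High Neck Angulation the baseline must fall "within the first 90 post-operative days for the High Neck Angulation Substudy".
- **5.2 (derivation).** From Core Lab data, "the measurement closest to 30 days after initial implant will be subtracted from the measurement closest to 365 days after initial implant". This is the only arithmetic given for the criterion. It has no window, no post-operative condition, no substudy distinction, no tie rule and no reference to 2.4.2.

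Three other places bear on it.

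- **4.2, Table 2** sets the analysis windows: 1 month, days 15-89; 6 months, days 90-242; 12 months, days 243-546; 24 months, days 547-911. The ideal windows are days 23-44, 150-210, 275-455 and 640-820.
- **5.1** requires, for inclusion by imaging, "both post-op (no later than one month study window) contrast-enhanced CT imaging" in Short Neck and "both post-op (no later than 90 days) contrast-enhanced CT imaging" in High Neck Angulation, each with a 12 month contrast CT. A High Neck Angulation subject without that CT may enter on a later one. The events to be ruled out on the later scan do not include enlargement.
- **5.4.2** counts effectiveness events by reference to 2.4.2.

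**The concern.** A programmer who codes 5.2 and one who codes 2.4.2 can get different enlargement results for the same subject. A subject can have a 12 month CT inside the analysis window, enter the effectiveness population because of it, and still have enlargement computed from the 6 month scan, because that scan lies nearer to day 365. Growth that reaches 5 mm between the two scans is a failure under 2.4.2 and not under 5.2. In a single-arm test against a fixed 80% goal, a missed failure favours the device.

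**Working it through.** The documents give no figure on this point to reproduce. The check compares scan days under the 5.2 rule, using the Table 2 windows.

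**1. When a 6 month scan wins.** Let s be the day of the 6 month scan and t the day of the 12 month scan. If t is at or before day 365, the 12 month scan is always nearer. If t is later, 5.2 takes the 6 month scan when 365 - s < t - 365, that is, when t > 730 - s.
- As t is at most 546, s must be at least 185.
- As s is at most 242, t must be at least 489.

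**2. Examples.**
- s = 210, t = 530: the distances are 365 - 210 = 155 and 530 - 365 = 165, so the 6 month scan is used.
- s = 210 displaces any 12 month scan on days 521-546 (26 days).
- s = 242, the extreme case, displaces days 489-546: 546 - 489 + 1 = 58 of the 304 days in the window.

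**3. How much of the windows is affected.** These are counts of day-pairs, not probabilities.

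| 6 month scan | 12 month scan | Pairs | 6 month scan chosen |
|---|---|---|---|
| analysis window | analysis window | 153 × 304 = 46,512 | 58 × 59 / 2 = 1,711 (3.7%) |
| ideal window | analysis window | 61 × 304 = 18,544 | 26 × 27 / 2 = 351 (1.9%) |
| analysis window | ideal window | 153 × 181 = 27,693 | 0 |
| ideal window | ideal window | 61 × 181 = 11,041 | 0 |

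The zeros follow because a 12 month scan in its ideal window is at most 90 days from day 365, while a 6 month scan is at least 365 - 242 = 123 days away. In the first row a further 59 pairs are exact ties (s + t = 730), for which 5.2 has no rule.

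**4. Direction of the substitution.** The earliest 24 month scan, day 547, is 182 days from day 365. The latest 12 month scan, day 546, is 181 days away. A 24 month scan therefore never displaces a 12 month scan, and any substitution is by an earlier scan.

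**5. Follow-up time.** At 365/12 = 30.4 days per month, days 185-242 are about 6-8 months after implant and days 489-546 about 16-18 months.

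**6. High Neck Angulation subjects without a 12 month CT.** If the choice is between a 6 month and a 24 month scan, 5.2 takes the 6 month scan in all 61 × 181 = 11,041 ideal-window pairs and in 51,380 of 153 × 365 = 55,845 analysis-window pairs (92%).

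**7. Baseline.** Read literally, a pre-treatment scan b days before implant is nearer to day 30 than a post-operative scan on day t when 30 + b < t - 30, that is, t > 60 + b. With the 1 month analysis window this needs t in days 61-89 and b from 0 to 28: 29 × 30 / 2 = 435 of 91 × 75 = 6,825 pairs (6.4%). It never happens for a post-operative scan in the ideal window, days 23-44.

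**8. What one subject can do.** SAP 5.4 uses the one-sided exact 95% lower bound, the 0.05 quantile of Beta(x, n - x + 1), against 0.80. If all subjects are evaluable:
- Short Neck: 71/80 gives 0.812 (met); 70/80 gives 0.797 (not met).
- High Neck Angulation: 83/95 gives 0.803 (met); 82/95 gives 0.791 (not met).

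**The case against.** The strongest reply is that 2.4.2 governs. Section 5.4.2 counts events that meet the 2.4.2 definition, 5.1 points to 2.4.2 for eligible events, and 5.2 can be read as choosing the nearest scan among those already inside the windows. This stands in part: it would be wrong to infer that the plan has no window for enlargement. But 5.4.2 says which definition an event must meet, not how the change in diameter is computed. Only 5.2 does that, and it does not send the programmer back to 2.4.2.

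A reader might also infer that a pre-treatment scan will commonly serve as baseline, since the protocol summary asks for "Contrast enhanced spiral CT of the abdomen and pelvis ≤ 90 days from procedure". The documents do not support this. Section 2.4.2 says post-operative for High Neck Angulation, 5.1 requires a post-operative CT for inclusion by imaging in both substudies, and nothing says that the Core Lab measures pre-treatment scans. What remains is that the Short Neck baseline sentence has only an upper limit and that 5.2 does not say post-implant.

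Three further objections are fair. The affected 12 month scans are at least 489 - 455 = 34 days past the ideal window. The direction of error is not certain, because an earlier scan could show enlargement that a later one does not. The cut-off contrast in step 8 applies to any single misclassified subject and does not measure this defect.

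Finally, only the protocol summary is available here and parts of the SAP are not shown, so a scan-selection convention may exist elsewhere.

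**Conclusion.** The point holds as an unreconciled difference between 5.2 and 2.4.2 on a primary failure criterion. Section 5.2 states a rule that, coded as written, can depart from the defined endpoint, so this is more than missing detail.

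Its reach is small. It needs a 6 month scan on days 185-242 together with a 12 month scan on days 489-546. A reader might take it to affect subjects with a 12 month CT in general, but no subject scanned in the 12 month ideal window is affected. How many subjects fall in the affected corner cannot be told from the documents, so no effect on the success rate can be estimated. One reclassified subject matters only if the count sits at 71/80 or 83/95.

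The conclusion assumes that 5.2 is coded literally and that no other text restricts the scans. The post-implant condition on baseline is a secondary clarification. The point should be corrected, but it does not call the design into question.

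**What to change.** In SAP 5.2, state that:

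- **Follow-up** is the Core Lab diameter closest to day 365 among scans in the 12 month analysis window, days 243-546.
- **Baseline** is the post-implant Core Lab diameter closest to day 30 within the 2.4.2 baseline window of that substudy. For Short Neck, say whether the one month window means the ideal or the analysis column of Table 2.
- **Ties** are broken by a stated rule.
- **High Neck Angulation subjects admitted under 5.1 on a post-12 month CT** take their follow-up diameter from that same CT, so that a 6 month scan does not stand in. This must be written as an explicit exception, because a filter to days 243-546 alone would leave these subjects without a follow-up diameter.

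With the 2.4.2 windows and the post-implant condition in place, no day-pair selects a 6 month scan over an in-window 12 month scan, or a pre-treatment scan over a post-operative baseline.

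The cost is a short addition to the SAP and a date filter in the program, with no new data. The success rate may come out slightly less favourable.

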5.3 Timing of Analyses

The primary effectiveness endpoint in the Short Neck Substudy will be analyzed after all Subjects eligible for the Short Neck Substudy Effectiveness Population have completed a follow-up visit in the 12 month window.

The primary effectiveness endpoint in the High Neck Angulation Substudy will be analyzed after all Subjects eligible for the High Neck Angulation Substudy Effectiveness Population have completed a follow-up visit in the 12 month window.

The primary safety endpoint will be analyzed in each substudy during the effectiveness analysis for that substudy.

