2.5.2 Primary Effectiveness Endpoint (each substudy)

The analysis of the primary effectiveness endpoint is intended to test the hypothesis that the effectiveness of the CEXC Device exceeds the performance goal of 80% freedom from effectiveness endpoint events in each substudy separately.

[figure not shown]
The hypotheses are specified as follows:

$$H_0: P_{EE} \le 0.80$$

 $H_A: P_{EE} > 0.80$

Doc Type: GC

2.6 Sample Size Assumptions For the Short Neck Substudy primary safety endpoint, a one sided test with alpha = 0.05, For the High Neck Angulation Substudy primary safety endpoint, one sided test with alpha = 0.05, For the Short Neck Substudy primary effectiveness endpoint, one sided test with alpha = 0.05, For the High Neck Angulation Substudy primary effectiveness endpoint, one sided test with alpha = 0.05, 2.7 Sample Size Calculations 80 Subjects will be utilized in the Short Neck substudy. The High Neck Angulation substudy sample size of 95 Subjects will be utilized.

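### The High Neck effectiveness population has no stated closing date: SAP 5.3 triggers on 12 month visits while SAP 5.1 admits subjects on later event-free CTs, so the denominator depends on the run date

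*SAP*

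**What the plan says.** - **Trigger.** SAP 5.3 times the High Neck effectiveness analysis for after "all Subjects eligible for the High Neck Angulation Substudy Effectiveness Population have completed a follow-up visit in the 12 month window". SAP 4.2, Table 2, sets the 12 month analysis window at days 243 to 546. This is an earliest time; the section gives no data cut.
- **Population.** SAP 5.1 requires a post-operative contrast CT and a 12 month visit with contrast CT, then adds a second route for High Neck only: "If a subject without a 12 month contrast-enhanced CT imaging has post-12 month contrast-enhanced CT imaging at which there was no endpoint event". The events checked are Type I endoleak, Type III endoleak, migration and rupture. The scan is chosen by "using the post 12-month contrast CT closest to the 12-month window, the subject will also be included in the analysis". No latest day is given. Short Neck has no such route.
- **Event route.** A third sentence, beginning "Additionally, any Subjects with an eligible effectiveness", brings in anyone with an eligible event whatever their imaging.
- **Test.** SAP 5.4: "One-sided exact Clopper-Pearson confidence intervals for binomial proportions (alpha=0.05) will be constructed". The decision rule is "The null hypothesis will be rejected if the lower bounds of the 95% confidence interval estimating device effectiveness and safety exceeds the performance goal". SAP 2.5.2 sets the goal at 80%.
- **Calendar.** The Protocol Summary gives "Subject accrual – 2 years". After 12 months, contrast CTs are annual. The 24 month window is days 547 to 911, and the 60 month window ends on day 2006.

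**The concern.** The two sections settle the same population by different clocks. A subject who attended at 12 months without contrast CT satisfies the 5.3 trigger, but the scan that decides membership may not yet exist. A subject with no visit in the window can be admitted by 5.1 yet can never satisfy 5.3 read literally. At any run date, early enrollees with a missing 12 month CT may already have a later scan, while late enrollees with the same gap do not.

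This matters because the later-CT route works in one direction. A late scan free of the four events brings the subject in, almost always as a success. A late scan showing an endoleak, for example, leaves the subject out, because SAP 2.4.2 counts endoleaks only within the 12 month window. A later run therefore tends to raise the success proportion, and this test decides half of High Neck substudy success (SAP 1.1.2).

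**Working it through.** **Inputs.** From the SAP: n = 95, goal 0.80, one-sided alpha 0.05, exact Clopper-Pearson bound, and the Table 2 windows. From the Protocol Summary: 24 months of accrual. Assumed, because the documents do not give it: M, the number of High Neck subjects without a 12 month contrast CT.

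**The plan's own figure.** The sample size of 95 cannot be reproduced, because the assumed success rate, power and attrition are not in the available text. The decision rule can be. The lower bound for x successes in n is the 0.05 quantile of Beta(x, n − x + 1), and the test passes if this exceeds 0.80. At n = 95 that needs at least 83 successes (bound 0.8034), with exact type I error 0.0424.

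**Step 1: how many entrants change the verdict.** The smallest n that passes is 76 with 9 failures, 82 with 10, 88 with 11 and 94 with 12. Hence:

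| Before | Bound | After | Bound | Added successes |
|---|---|---|---|---|
| 76/87 | 0.7994 (fail) | 77/88 | 0.8016 (pass) | 1 |
| 81/93 | 0.7993 (fail) | 82/94 | 0.8014 (pass) | 1 |
| 75/86 | 0.7972 (fail) | 77/88 | 0.8016 (pass) | 2 |

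An added success never turns a pass into a fail. An entrant who fails on enlargement can: 77/89 has bound 0.7907.

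**Step 2: chance of passing at a true rate of 0.80.** Let q be the fraction of the M subjects whose late CT exists at the run date. Event-free scans enter as successes and the others stay out:

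P(pass) = Σₓ Σₛ Bin(x; 95 − M, 0.80) · Bin(s; M, 0.80q) · 1[bound(x + s, 95 − M + s) > 0.80]

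| M | q = 0 | q = 0.5 | q = 1 |
|---|---|---|---|
| 5 | 0.038 | 0.041 | 0.061 |
| 10 | 0.033 | 0.058 | 0.080 |

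At a true rate of 0.85, waiting for all late CTs turns a fail into a pass with probability 0.09 (M = 5) or 0.18 (M = 10).

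The model takes missingness as unrelated to outcome and lets every failure among the M subjects drop out. In practice, failures through technical failure, rupture or conversion within the window, or enlargement would still count. For a given M, the figures therefore lean high.

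**Step 3: the same calculation with late CTs counted whatever they show.** With all 95 in, type I error is 0.0424. Taking the better of two cuts (half the late CTs in, then all) gives 0.044 for M = 5 and 0.048 for M = 10.

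**Step 4: how many are still outstanding at the trigger.** Assume uniform accrual.
- Run at month 36 (24 + 12), late CTs at 24 months: (36 − 24)/24 = 50% already have one, leaving 5 of 10.
- Run when the last subject's window closes, day 546 or about month 18, so month 42 (24 + 18): (42 − 24)/24 = 75%, leaving 2.5 of 10.
- Same run date, with late CTs at the start of the ideal 24 month window (day 640, about month 21): (42 − 21)/24 = 87.5%, leaving about 1.3 of 10.

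**The case against.** Four points have force.

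1. A reader might infer that an unfixed run date inflates the type I error by itself. Step 3 does not support that: with result-independent entry, even the better of two cuts stays below 0.05. The excess needs event-free-only entry. What stands is that the open cut lets that excess vary with the run date.
2. A reader might infer that the sponsor intends to choose its cut. The documents do not say so. SAP 5.3 describes one analysis per substudy, SAP 6.0 says board reviews are not statistical analyses, and nothing provides for re-running the test. The point is that the rule leaves the population undefined; it makes no claim about intent.
3. The route is narrower than any later scan. It needs a contrast CT, the one nearest the window, free of four events. Once a subject's first late contrast CT exists, later ones do not change which is read, and follow-up itself ends at day 2006. The open question is only whether that first scan exists at the run date. Step 4 shows that the number outstanding may be only one or two in ten, but one can be enough at a boundary result.
4. Much of SAP 5.5, 7 and 8 and the protocol body is not in the available text. A lock date or a sensitivity analysis could sit there. If so, 5.3 should cite it.

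**Conclusion.** The point holds in a limited form. In the available text, the 5.3 trigger does not fit the 5.1 population, and the High Neck denominator is not fixed until a run date is chosen. With a true rate of 0.80 and 5 to 10 of 95 subjects lacking a 12 month contrast CT, the chance of a false pass ranges from 0.033–0.038 with no late CTs to 0.061–0.080 with all of them. SAP 5.4 claims less than 0.05. The size rests on the assumed M and on missingness unrelated to outcome, and it belongs jointly to event-free-only entry and the open cut. The documents do not support attributing it to timing alone. The verdict is at risk only near the boundary, where one or two entrants are enough.

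**What to change.** **Preferred.** Keep the 12 month trigger in SAP 5.3. In SAP 5.1, make the High Neck population without the later-CT route primary, and report the route as a sensitivity analysis. This removes both the timing mismatch and the one-way entry.

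**If the route stays primary.** State in 5.1 and 5.3 one data cut and a latest CT day (for example day 911, the end of the 24 month window). Count every qualifying late contrast CT whatever it shows, and do not update membership after the cut. For a fixed n from 60 to 95, exact type I error is then at most 0.0490. A cut-off or a wait alone is not enough: waiting for all late CTs under the present entry rule is the q = 1 column, 0.061 to 0.080.

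**Cost.** SAP wording only. The preferred form loses a few subjects from the primary population. If the true rate were 0.90 (assumption), power would be 0.81 at n = 90 or 0.77 at n = 85, against 0.85 at n = 95. Keeping the route costs some delay instead, up to about a year.
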